3.4.4 Accountability of Investigational Products

The PI/ designee are responsible for accountability of all trial drug supplies (used/unused) at the site. During on-site monitoring visit, the study monitor/CRA will verify receipt of investigational product, returned and empty vials/cartons, batch numbers of used vials, and will conduct an inventory of remaining clinical trial supplies at the site close-out visit. All trial drug inventories must be made available for inspection by the monitor, sponsor representatives and regulatory agency inspectors/monitor upon request.

Following monitor/CRA verification and instruction, expired or unused trial drugs can be returned to the sponsor or destroyed according to local institutional policy with sponsor pre-approval of a site-specific destruction policy. Certificate(s) of destruction or documentation of destruction must be filed at the site and in Trial Master File. Used, returned trial drugs can be destroyed according to local institutional policy with sponsor pre-approval of a site-

specific destruction policy. Certificate(s) of destruction or documentation of destruction must be filed at the site and in the Trial Master File.

3.4.5 Precautions and Risks Associated with Investigational Products

3.4.5.1 Tenalisib

Monitoring of liver enzymes and levels of TSH, T3, and T4 in subjects receiving Tenalisib is recommended based on target organ toxicity. Patients will be monitored for increased ALT/AST, skin rash, neutropenia as these are reported with Tenalisib. In addition, enteritis (colitis), pneumonia/pneumonitis as these events are reported with other PI3K inhibitors.

Tenalisib elicits no photo instability upon exposure to ultraviolet (UV) radiations. However, in absence of in vitro data, possibility of photo-toxicity with Tenalisib cannot be ruled out.

Tenalisib shows inhibition of CYP3A4 enzyme. Therefore, concomitant administration of Tenalisib with predominant CYP3A4 substrates (e.g. calcium channel blockers, warfarin, carbamazepine, macrolide antibiotics, lovastatin, simvastatin, terfenadine) may reduce clearance of these drugs increasing the risk of adverse events. Similarly, as Tenalisib is inhibited by CYP3A4/5 and CYP2C9, there is possibility of drug interaction with inhibitors or inducers of CYP3A4 and CYP2C9. If concomitant treatment of these drugs are clinically warranted, careful observation of the patient is advised. Strong inhibitor or inducers should be avoided as directed in Section on prohibited medication. Please refer to the recent Investigator Brochure for additional safety information.

3.4.5.2 Romidepsin

The following adverse events have been reported in patients receiving Romidepsin:

- Myelosuppression: Romidepsin can cause thrombocytopenia, leukopenia (neutropenia and lymphopenia), and anemia; monitor blood counts during treatment with Romidepsin; interrupt and/or modify the dose as necessary.
- Fatal and serious infections, including pneumonia, sepsis, and viral reactivation, including Epstein Barr and Hepatitis B viruses, have been reported in clinical trials with Romidepsin. These can occur during treatment and within 30 days after treatment. The risk of life-threatening infections may be greater in patients with a history of prior treatment with monoclonal antibodies directed against lymphocyte antigens and in patients with disease involvement of the bone marrow.
- Several treatment-emergent morphological changes in ECGs (including T-wave and ST-segment changes) have been reported in clinical studies. The clinical significance of these changes is unknown.
- Tumor lysis syndrome (TLS) has been reported to occur in 1% of patients with tumor stage CTCL and 2% of patients with Stage III/IV PTCL. Patients with advanced stage disease and/or high tumor burden are at greater risk, should be closely monitored, and managed as appropriate.
- Since Romidepsin is a substrate of CYP3A4 enzymes, concomitant administration of CYP3A4 inhibitor or inducer may interact with Romidepsin. If concomitant treatment of these drugs is clinically warranted, careful observation of the patient is advised.

Strong inhibitor or inducers should be avoided as directed in Section on prohibited medication.

Please refer to the full prescribing information of Romidepsin for additional safety information.

3.5 The Expected Duration of Subject Participation and Follow-up

The expected duration of subject participation in the study will be about 8 months. Post C8D1, patients with no evident disease progression will be given the opportunity to enroll in an open-label compassionate use study protocol and will be followed up.

3.6 Study Stopping Rules

3.6.1 Stopping Rule for Dose Escalation

The SRC will be in charge of reviewing safety data following the final treatment dose (Day 28 of Cycle 1) of the last patient in each cohort and will decide whether or not it is possible to proceed to the next cohort according to the dose escalation procedure described in Section 3.2.1.1. In order to ensure safety and limit toxicity for enrolled patients, dose modifications will be performed according to the procedure described in Section 7.7.

3.6.2 Suspension of Patient Enrollment

In the event of one (1) death attributed to the study drug, study accrual will be suspended pending further investigation, and will only be resumed at the recommendation of the SRC. The SRC will have discretion to terminate the trial if an additional death occurs that can be attributed to the study drug.

3.6.3 Stopping Rule for Dose Expansion

After establishing the MTD/optimal dose, the Phase II expansion part will be opened as approved by the SRC. The SRC will continue to monitor safety of the combination (or toxicity trends that may be of concern) at interval of 3 months from initiation of expansion cohort till the completion of the study. Safety/toxicity will be monitored across cohorts combined together. The SRC will have discretion to terminate the trial if there are major safety concerns.

3.6.4 Study Stopping

Sponsor reserves the right to terminate the study in the interest of patient safety, for non-compliance with the protocol, lack of recruitment or any other administrative reasons. The sponsor and PIs will notify the regulatory authority and respective IRB(s) respectively if the trial terminates early with a justification for the early termination.

4 SELECTION AND WITHDRAWAL OF SUBJECTS

4.1 Inclusion Criteria

1. Age ≥ 18 years on the day of signing informed consent.
2. Pathologically confirmed T-cell lymphoma at the enrolling institution*.
3. Disease status as defined as relapsed after or refractory to at least one systemic therapy.

4. The patients should have received NOT more than three prior systemic combination chemotherapies.
5. Must have ECOG performance status ≤ 2 .
6. PTCL patients must have measurable disease as defined at least one bi-dimensional measurable lesion with minimum measurement of > 1.5 cm in the longest diameter.
7. Life expectancy of at least 3 months.
8. Toxicities related to prior therapy must have returned to **Grade 1 or less**, except for alopecia.
9. Adequate bone marrow, liver and renal function in line with below mentioned laboratory requirements. Hemoglobin and platelet requirements should not be met by use of recent transfusion or growth factor support (GCSF or erythropoietin) within 3 weeks prior to treatment initiation.
 - Hemoglobin ≥ 8.0 g/dL
 - Absolute neutrophil count (ANC) $\geq 1,000/\mu\text{L}$
 - Platelet count $\geq 75,000/\mu\text{L}$
 - Total bilirubin ≤ 1.5 times the ULN (or $\leq 3 \times$ ULN, if patient has Gilbert syndrome)
 - AST (SGOT) and ALT (SGPT) $\leq 3 \times$ ULN; ≤ 5 ULN in case of liver involvement
 - Calculated creatinine clearance (CrCl) > 50 ml/min by Cockcroft-Gault formula.
10. Use of an effective means of contraception for women of childbearing potential and men with partners of childbearing potential.
11. Female subject of childbearing potential should have a negative urine or serum pregnancy within 72 hours prior to receiving the first dose of study medication. If the urine test is positive or cannot be confirmed as negative, a serum pregnancy test will be required.
12. Provide written informed consent prior to any study-specific screening procedures.
13. Willingness and capability to comply with the requirements of the study.

*Note: The EORTC classification of CTCLs will be used to classify patients. CTCL includes other variants other than MF (e.g. Gamma delta cutaneous T-cell lymphoma or subcutaneous or panniculitis like T-cell lymphoma and CD8 positive T-cell lymphoma). PTCL includes patients with predominantly nodal disease (systemic involvement) but some patients (e.g. AITCL or ATCL) may have skin lesions. Patient having both skin and node lesions will be placed into one of the group (CTCL or PTCL) as approved by investigator.

4.2 Exclusion Criteria

1. Patient receiving anticancer therapy including any investigational therapy (e.g. chemotherapy, biologic therapy, hormonal therapy, surgery, radiotherapy (except limited field palliative radiation) and/or tumor embolization) ≤ 3 weeks or 5 half-lives (whichever is shorter) prior to C1D1.
2. Patient who discontinued prior therapy with PI3K inhibitors or HDAC inhibitors due to drug toxicity.
3. PTCL patients with Allo-SCT on active GVHD or immunosuppression therapy within 3 months prior to C1D1. CTCL patients with the history of Allo-SCT will be excluded.
4. Patient with any medical conditions requiring the use of systemic immunosuppressive medications (> 20 mg/day of prednisone or equivalent).

5. Severe bacterial, viral or mycotic infection requiring systemic treatment.
6. Pregnancy or lactation.
7. History of chronic liver disease, hepatic veno-occlusive disease, or current alcohol abuse.
8. Known clinically active central nervous system (CNS) or meningeal involvement. (Note: In the absence of symptoms, investigation into CNS involvement is not required. Patients are eligible if metastases have been treated and patients are neurologically returned to baseline or neurologically stable for at least 4 weeks prior to C1D1).
9. Known seropositive requiring anti-viral therapy for human immunodeficiency virus **(HIV) infection.**
10. Known seropositive requiring anti-viral therapy for hepatitis B virus (HBV) infection **OR** evidence of **active hepatitis B infection** as defined by detectable viral load if the antibody tests are positive. [Note: A positive HBcAb subject with an undetectable/negative hepatitis B DNA test (e.g., polymerase chain reaction [PCR] test) can be enrolled]
11. Known seropositive requiring anti-viral therapy for hepatitis c virus (HCV) infection **OR** patients with positive hepatitis C virus Ab.
12. Subjects with active EBV unrelated to underlying lymphoma (positive serology for anti-EBV VCA IgM antibody and negative for anti-EBV EBNA IgG antibody), or clinical manifestations and positive EBV PCR consistent with active EBV infection.
13. Subject with active CMV (positive serology for anti-CMV IgM antibody and negative for anti-CMV IgG antibody and positive CMV PCR with clinical manifestations consistent with active CMV infection) and requiring therapy. [Note: Carriers will be monitored per institutional guidelines.]
14. Subjects with concomitant second malignancies (except adequately treated non-melanomatous skin cancers, ductal carcinoma in situ, superficial bladder cancer, prostate cancer or in situ cervical cancers) are excluded unless a complete remission is achieved at least 2 years prior to study entry and no additional therapy (except adjuvant or maintenance therapy to reduce the risk of recurrence) is required or anticipated to be required during the study period.
15. Administration of any of the following within 1 week prior to C1D1:
 - Strong inhibitors or inducers of CYP3A4 including but not limited to grapefruit products, herbal supplements and drugs
 - Strong inhibitors or inducers of CYP2C9 including but not limited to herbal supplements and drugs
 - Substrates of CYP3A4 enzyme with a narrow therapeutic range.
16. History of Grade 4 anaphylactic reaction.
17. Administration of live vaccines within 6 weeks of C1D1.
18. History of prior surgery or gastrointestinal dysfunction that may affect drug absorption (e.g., gastric bypass surgery, gastrectomy)
19. Current history of a serious uncontrolled medical disorder, metabolic dysfunction, physical examination findings, or clinical laboratory findings giving reasonable suspicion of a disease or condition that contraindicates use of an investigational drugs or render the subject at high risk from treatment complications.
20. Uncontrolled or significant cardiovascular disease including, but not limited to:

- Congenital long QT syndrome.
- QTcF interval > 450 msec
- Myocardial infarction or stroke/TIA within the past 6 months
- Uncontrolled angina within the past 3 months
- Significant ECG abnormalities including 2nd degree atrio- ventricular (AV) block (AV) block type II, 3rd degree AV block
- History of clinically significant arrhythmias (such as ventricular tachycardia, ventricular fibrillation or torsades de pointes)
- History of other clinically significant heart disease (ie, cardiomyopathy, congestive heart failure with NYHA functional classification III-IV, pericarditis, significant pericardial effusion)
- Requirement for daily supplemental oxygen therapy.

4.3 Discontinuation from Trial Treatment

The following events may be considered sufficient reason for discontinuing treatment with the study medication:

- NCI CTCAE v5.0 Grade 3/4 non-hematological toxicity related to study drug that necessitate withdrawal in the opinion of investigator
- Development of an intercurrent illness, condition or procedural complication, which could interfere with the patient's continued participation.
- Voluntary patient withdrawal from study treatment (all patients are free to withdraw from participation in this study at any time, for any reasons, specified or unspecified, and without prejudice).
- Any other situation where, in the opinion of the investigator, continued participation in the study would not be in the best interest of the patient
- Disease progression during therapy
- Study completion

5 TREATMENT OF SUBJECTS

5.1 Administration of Tenalisib

Tenalisib will be administered orally twice daily in 28-days cycle (Day 1-28) up to C8D1 unless progression of disease or toxicity warranting discontinuation of therapy. Only during Cycle 1 of Dose Escalation, Tenalisib will be given starting from Day 3. Thus, patients will receive Tenalisib for 25 days in the first cycle of Dose Escalation. Please refer to Section 3.4.3 for administration of Tenalisib.

5.2 Administration of Romidepsin

Romidepsin will be administered intravenously (IV) over a 4-hour period on days 1, 8 and 15 of a 28-day cycle. Please refer to Section 3.4.3 for administration of Romidepsin.

5.3 Concomitant Medications

- Antimicrobial and anti-viral prophylaxis should be used according to local standard practice; PCP and Zoster prophylaxis is strongly recommended.
- G-CSF and other hematopoietic growth factors may be used for the management of acute

toxicity such as febrile neutropenia when clinically indicated or at the discretion of the investigator.

- Transfusions may be given, based on standard criteria and clinical judgment.
- No prophylaxis will be given for Tenalisib. However, patient may receive prophylactic anti-emetics for Romidepsin at the discretion of the investigator.
- Patient may receive prophylactic allopurinol, in case risk of tumor lysis syndrome.
- Low doses of steroids are allowed if it stabilized at < 20 mg per day of prednisone or equivalent and started at least 7 days prior to first dose.
- Patients are permitted to use of topical, ocular, intra-articular, intranasal, and inhaled corticosteroids (with minimal systemic absorption). A brief (less than 4 weeks) course of corticosteroids for treatment related AE is permitted.
- Inactivated seasonal influenza vaccine can be given to subjects before treatment and while on therapy without restriction.
- If concomitant treatment of drugs metabolized by CYP3A4 enzymes are clinically warranted, careful observation of the patient is advised. Use of heparin or warfarin for prophylaxis and treatment of venous thrombosis is prohibited. Low molecular weight heparin (LMWH) is acceptable. Similarly, Dabigatran and Edoxaban, Direct-acting Oral Anti-Coagulants (DOAC) class of drugs, are acceptable as they are not metabolized by CYP3A4/CYP2C9 enzymes.
- Patients should be warned about the possible photosensitivity and advised to be careful with the UV exposure while on Tenalisib treatment. Patients should be recommended to wear loose-fitting clothes that protect skin from sun exposure, in case they need to be outdoors. If sunburn like reaction or skin eruption occurs, patients should contact study physician.

5.4 Prohibited Medications

The following treatments are prohibited while on the clinical trial:

- Any other anti-lymphoma therapy (e.g. radiation therapy, hormonal therapy for cancer, cancer immunotherapy or other biologic therapy).
- Herbal preparations/medications are not allowed throughout the trial. Patients should stop using these herbal medications at least 7 days prior to C1D1.
- Strong inhibitors or inducers of CYP3A4, including grapefruit products, herbal supplements and drugs (e.g. atazanavir, clarithromycin, indinavir, itraconazole, ketoconazole, nefazodone, neflifinavir, ritonavir, saquinavir, telithromycin and rifampicin). Patients should stop using these medications at least 7 days prior to C1D1.
- Strong inhibitors or inducers of CYP2C9, including herbal supplements and drugs (e.g. fluconazole and rifampicin). Patients should stop using these medications at least 7 days prior to C1D1.
- Substrates of CYP3A4 enzyme with a narrow therapeutic range (e.g. Warfarin and phenytoin, alfentanil, astemizole, cisapride, cyclosporine, diergotamine, ergotamine, fentanyl, pimozide, quinidine, sirolimus, tacrolimus, terfenadine). Patients should stop using these medications at least 7 days prior to C1D1.
- Use of heparin or warfarin for prophylaxis and treatment of venous thrombosis is prohibited. Similarly, Apixaban and Rivaroxaban, DOAC class of drugs, are also prohibited they are metabolized by CYP3A4 enzymes. These drugs should be stopped at

least 7 days prior to C1D1.

- Live attenuated vaccine (e.g. Flu vaccine, pneumovax, varicella)
- Steroids > 20 mg unless for management of toxicity.

Discontinuation of patient who received concomitant/prohibited medication will be taken by the PI in consultation with Medical Monitor on case to case basis, after reviewing ongoing clinical benefit and risk. The decision to allow a patient to continue will be documented and archived at the site and at Rhizen.

5.5 Procedures for Monitoring Subject Compliance.

The following measures will be employed to ensure treatment compliance.

5.5.1 Tenalisib

Subjects will be instructed to bring any unused study drug to the site at each visit. Research personnel will count and record the number of used and unused study drug tablets at each visit. The study coordinator will question the patient regarding adherence to the dosing regimen, record the number of tablets and strengths returned, the date returned and determine treatment compliance before dispensing new medication to the study patient. Compliance below 80% will require counseling of the patient by study site personnel.

5.5.2 Romidepsin

Administration of trial medication will be documented by the investigator and/or trial staff as per institutional practice. The total volume of treatment infused will be compared to the total volume prepared to determine compliance with each dose administered. Compliance with trial treatment will be measured by number of Romidepsin infusion.

6 TRIAL ASSESSMENT AND PROCEDURE

6.1 Overview

The Schedule of Event (Table 5 and Table 6) summarizes the trial procedures to be performed at each visit and is divided into following.

1. Screening (Day -28 to Day 0)
2. On treatment procedures (C1D1 to C7D28)
3. End of Treatment (C8D1 or within 7 days from the last dose)
4. End of Study (Day +30 from the last dose)

Individual trial procedures are described in detail below. It may be necessary to perform these procedures at unscheduled time points if deemed clinically necessary by the investigator. Multiple procedures may be scheduled at the same time point relative to Tenalisib. Priority should be given to PK collection at the time specified and vital signs should be performed prior to blood collections.

6.2 Informed Consent

The investigator or qualified designee must obtain documented written consent from each potential subject or each subject's legally acceptable representative prior to participating in a clinical trial. Consent must be documented by the subject's dated signature or by the

subject's legally acceptable representative's dated signature on an IRB-approved consent form along with the dated signature of the person conducting the consent discussion. A copy of the signed and dated consent form should be given to the subject before participation in the trial.

The initial informed consent form, any subsequent revised written informed consent form and any written information provided to the subject must receive the IRB/IEC's approval/favorable opinion in advance of use. The subject or his/her legally acceptable representative should be informed in a timely manner if new information becomes available that may be relevant to the subject's willingness to continue participation in the trial. The communication of this information will be provided and documented via a revised consent form or addendum to the original consent form that captures the subject's dated signature or by the subject's legally acceptable representative's dated signature. Specifics about a trial and the trial population will be added to the consent form template at the protocol level. The informed consent will adhere to IRB/IEC requirements, applicable laws and regulations and Sponsor requirements.

6.3 Screening

Written informed consent must be obtained ≤ 30 days prior to the initiation of trial treatment and before any protocol-specific procedures are performed. (The first day of trial treatment will be considered as C1D1.) Patients should be re-consented in the case that informed consent is obtained >30 days prior to the initiation of trial treatment. Screening vitals, laboratory tests, as described in the Schedule of Events, will be performed as per institutional practice and will be reviewed by the site PI/designee. The laboratory tests should be done ≤ 7 calendar days prior to the initiation of trial treatment. Re-screening can be done at the discretion of PI. Scans and other investigations to document measurable disease should be performed within 28 days prior to C1D1.

Lymphoma diagnosis should be made on the basis of morphology, immunohistochemistry, and flow cytometry reviewed by an experienced lymphoma pathologist. Appropriate, molecular studies should be considered to accurately categorize the lymphoma. For CTCL, the histopathologic diagnosis should be confirmed in a skin biopsy representative of current disease by a pathologist with expertise in cutaneous lymphoma. For Sezary patients, the diagnosis should be based on skin and blood criteria (defined as meeting T4 plus B₂ criteria) ([Appendix D](#)).

Clinical assessments of patients will include ECOG performance status ([Appendix A](#)), lymph nodes, organomegaly, and "B" symptoms. The staging of NHL/HL and CTCL patients will be done according to Ann Arbor ([Appendix G](#)) and ISCL/EORTC criteria ([Appendix E](#)) respectively [10]. CTCL patients will have half body global and up to 5 selected representative index lesions photographed at baseline.

Table 3: Summary of Key Assessments at Screening

Procedures	PTCL	CTCL
Lab investigation	√	√
ECG	√	√
Bone marrow biopsy	√ ¹	In case of patients with blood involvement (B ₂) ²
Radiological assessment ³	√	In case of nodal/visceral involvement
Skin assessment (mSWAT)	-	√
Skin biopsy	-	√
Skin photograph	-	√
Biomarker	√	√

1. A bone marrow biopsy and/or aspirate should be collected ≤ 3 months prior to C1D1.
2. A bone marrow biopsy will be done unless it has been shown to be negative within the last 6 months.
3. The scan and other investigations to document measurable disease should be performed within 28 days prior to C1D1.

During screening, active infection with HBV, HCV, CMV, EBV or HIV should be ruled out. To be considered negative for active infection, following algorithm will be used:

- HBV: HBc antibody should be negative or if HBc antibody is positive, HBVDNA should be undetectable
- HCV: HCV antibody should be negative or if HCV antibody is positive, HCVDNA should be undetectable
- HIV: HIV antibody should be negative. (HIV 1/ 2 antibody should be negative unless positive result is considered false positive by PI)
- EBV: Negative for anti-EBV VCA IgM antibody or if anti-EBV VCA IgG antibody is positive, EBV DNA should be negative.
- CMV: Negative for anti-CMV IgM antibody or if positive anti-CMV IgG antibody is positive, CMV DNA should be negative. [Note: Carriers will be monitored per institutional guidelines.]

Note: Patients who show evidence of hepatitis B infection (HBsAg positive [regardless of antibody status] or HBsAg negative but anti-HBc positive), need to be evaluated for initiation of HBV antiviral prophylaxis and should be closely monitored for HBV reactivation.

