1.1.2 Summary of Clinical Evaluation

To date, Tenalisib has been evaluated in four clinical trials:

1. A Phase I Dose Escalation Study Evaluating the Safety and Efficacy of RP6530, a dual PI3K δ/γ inhibitor, in Patients with Relapsed or Refractory Hematologic Malignancies (European study: Protocol Number RP6530-1301) Status: Completed
2. A Phase I/Ib, Dose Escalation Study to Evaluate Safety and Efficacy of RP6530, a dual PI3K δ/γ inhibitor, in Patients with Relapsed or Refractory T-cell Lymphoma (US study: Protocol number RP6530-1401). Status: Recruitment completed. Study Ongoing
3. An open label, randomized, single dose, crossover study to evaluate food effects on relative bioavailability of RP6530 administered in fasting and fed conditions in healthy volunteers (Food effect study, Protocol no: RP6530-1501). Status: Completed
4. An Open label, Phase I/II study to evaluate the safety and efficacy of RP6530, a novel PI3K δ/γ dual inhibitor given in combination with an anti-PD-1 therapy, Pembrolizumab in adult patients with relapsed or refractory Classical Hodgkin's lymphoma (cHL). Status: Ongoing and currently recruiting.

- **Safety:**

In RP6530-1401 study, a total of 58 patients were treated at 200 mg BID (n=4), 400 mg BID (n=4), 800 mg BID (Fasting) (n=44) and 800 mg BID (Fed) (n=6) in both dose escalation and dose expansion cohorts. Tenalisib demonstrated acceptable safety and tolerability profile up to 800 mg BID (fasting). Tenalisib 800 mg BID (Fasting) was considered as MTD dose in patients with T-cell lymphoma. Majority of AEs include transaminitis, skin rash. Treatment related Grade ≥ 3 includes AST/ALT elevation (n=12), rash (n=4), hypophosphatemia (n=2), neutropenia (n=1), INR Increase (n=1), sepsis (n=1), pyrexia (n=1), diplopia secondary to neuropathy (n=1), drug reaction (n=1), and bacteremia (n=1). Treatment related SAE reported were pyrexia (n=1), raised INR (n=1), sepsis (n=1), diplopia secondary to neuropathy (n=1), drug reaction (n=1) and bacteremia (n=1).

- **Pharmacokinetics:**

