Hepatic*	Transaminitis Grade ≥ 1 Transaminitis ($ALT/AST > 1-3 \times$ ULN): • Maintain Tenalisib dose and initiate prednisone 40 mg daily .

	
 Monitor AST/ALT weekly until resolved and then taper steroid. Withhold Tenalisib in case of development of grade 2 transaminitis or worsening of Grade 1 transaminitis while on steroids. 
Grade \geq 3 Transaminitis (ALT/AST $>5-20$ X ULN):
 
 Withhold Tenalisib and monitor ALT/AST twice a weekly until Grade \leq 1; restart Tenalisib at one dose lower. Initiate prednisone 1 mg/kg in case no improvement with discontinuation of Tenalisib in 1 week. Monitor ALT/AST twice a weekly until Grade \leq 1; restart Tenalisib at one dose lower. and taper steroid. If no immediate response to steroids within 7 days, initiate mycophenolate mofetil. In case of recurrence of transaminitis at reduced doses, discontinue Tenalisib permanently after assessing risk versus benefit. 
Grade \geq 4 Transaminitis (ALT/AST >20 X ULN):
 
 Tenalisib should be permanently discontinued. 
Bilirubin:
 
 Grade \geq 2 ($> 1.5-3$ X ULN): Maintain Tenalisib dose. Monitor at least weekly until \leq 1X ULN Grade \geq 3 ($> 3-10$ X ULN): Withhold Tenalisib. Monitor at least weekly until bilirubin is \leq 1X ULN; restart Tenalisib at one dose lower. Grade \geq 4 (> 10 X ULN): Discontinue Tenalisib permanently
Infection	
Grade 3 or higher sepsis or pneumonia
 
 Interrupt Tenalisib until infection has resolved.
Diarrhea	
Moderate:
 
 Maintain Tenalisib dose. Monitor at least weekly until resolved. 
Severe diarrhoea or hospitalization
 
 Withhold Tenalisib dose. Monitor at least weekly until resolved. Restart Tenalisib at one dose lower. 
Life threatening diarrhoea
 
 Discontinue Tenalisib permanently.

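### Protocol 6.3 clears an HCV antibody-positive patient on an undetectable HCV DNA result, whereas exclusion 11 bars every antibody-positive patient; HCV DNA is also the wrong test for an RNA virus.

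*Protocol*

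**What the plan says.** Protocol 6.3 requires active HBV, HCV, CMV, EBV and HIV infection to be ruled out at screening and introduces its rules with "To be considered negative for active infection, following algorithm will be used". The HCV line has two branches. A patient passes with a negative antibody. For a patient with a positive antibody the condition is "if HCV antibody is positive, HCVDNA should be undetectable".

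Exclusion criterion 11 (Protocol 4.2, repeated in the synopsis) has two limbs joined by OR: known seropositive patients who need antiviral therapy for HCV, and "patients with positive hepatitis C virus Ab". Neither place adds an exception for viral load.

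For hepatitis B the protocol does write the exception down. A note to exclusion 10 allows "A positive HBcAb subject with an undetectable/negative hepatitis B DNA test" to be enrolled, and the HBV line in 6.3 says the same.

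On a separate matter, Table 4, Protocol 6.3 and exclusion 12 all call for EBV testing, but footnote 10 of Tables 5 and 6 lists only HIV, HBV, HCV and CMV as the serology.

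**The concern.** A site that screens an HCV antibody-positive patient finds two instructions that point in opposite directions, and nothing in 6.3 says which prevails. The test that is meant to settle the matter under 6.3 cannot do so, because a DNA assay does not detect an RNA virus.

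The point deserves attention because the liver is a known target of Tenalisib. Table 8 responds to the lowest grade of transaminase rise with "Maintain Tenalisib dose and initiate prednisone 40 mg daily". For Grade 3 or higher events it goes further: "If no immediate response to steroids within 7 days, initiate mycophenolate mofetil". A patient with unrecognised HCV viraemia would be exposed to that immunosuppression, and the infection would be a competing explanation for any rise in enzymes.

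**Working it through.** The plan states no figure on this point, so the check sets the rules side by side. Inputs: the HCV and HBV lines of Protocol 6.3; exclusions 10 and 11 in Protocol 4.2 and the synopsis; SAP 7.1 to 7.4. One fact comes from general virology and not from the documents: HCV is an RNA virus.

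**Step 1. Apply each rule to each kind of patient.**

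| Patient | 6.3 as written (DNA) | 6.3 if RNA was meant | Exclusion 11 |
|---|---|---|---|
| Antibody negative | negative for active infection | negative for active infection | not excluded by antibody |
| Antibody positive, no virus | negative for active infection | negative for active infection | excluded |
| Antibody positive, viraemic | negative for active infection | not negative | excluded |

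The second row is the contradiction. It does not depend on the analyte. The third row is the extra consequence of naming DNA: read literally, the condition is met by every antibody-positive patient, including one with active infection.

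**Step 2. Compare with hepatitis B.** The HBV line in 6.3 has the same structure, and the note to exclusion 10 matches it, so the two places agree. HCV has the branch in 6.3 without the matching note. The documents therefore do not show whether cleared HCV infection was meant to be eligible.

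**Step 3. Trace the effect on the analysis sets.**
- SAP 7.1 defines enrolled patients by reference to the inclusion and exclusion criteria, which contain the stricter rule.
- The safety set (SAP 7.2) needs one dose. The mITT set (SAP 7.3) needs one dose and a post-baseline efficacy assessment. Neither depends on eligibility, so neither changes.
- The PP set (SAP 7.4) leaves out major deviations, and enrolling an ineligible subject is a listed example. The medical monitor decides on inclusion before database lock. PP membership is the only set that could change.

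**Step 4. Safety background.** Protocol 1.1.2 reports 12 treatment-related AST/ALT elevations of Grade 3 or higher in the Tenalisib study in T-cell lymphoma, in which 58 patients were treated. If each count is a different patient, 12/58 = 20.7%. This explains why hepatic screening matters here. It measures neither the probability nor the consequence of the text error.

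**The case against.** The strongest reply is that 6.3 only defines active infection and does not say that a patient who passes may be enrolled. Eligibility is settled by 4.2. The two lists also differ for HIV, where 6.3 asks for a negative antibody (unless judged a false positive) while exclusion 9 bars only known seropositive patients who need therapy. Read as two gates that must both be passed, the stricter rule decides, and the HCV branch is redundant, not permissive. This is right about the outcome when both rules are applied. It does not rescue the wording: on that reading the branch has no function, and it still names a test that cannot do its job.

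A reader might infer that the protocol admits patients with active HCV. It does not. For that to happen, a site would have to overlook exclusion 11 and also act literally on a DNA result, where a laboratory would probably run RNA. Exclusion 7 (history of chronic liver disease), the bilirubin and transaminase limits in inclusion 9, and Chemistry Panel I on Days 1, 8, 15 and 22 of Cycles 1 and 2 narrow the exposure further, although none replaces an HCV test.

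A reader might also take 12/58 as the size of the problem, or infer that the response rate or the MTD is at risk. The first is background toxicity from another study. The second would need the same chain of slips, and the documents give no basis for putting a probability on it.

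Finally, the analyte looks like a carry-over from the HBV line directly above. That is plausible, but the line is an operative screening instruction and should be correct.

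**Conclusion.** The contradiction between Protocol 6.3 and exclusion 11 is real and is shown by the documents alone. The wrong analyte is a second error in the same line; it rests on elementary virology and is not needed for the first.

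The practical size is small. Exclusion 11 governs when both rules are applied, so the exposure is limited to a site that relies on 6.3 alone. No frequency can be given for that. No sample size or error rate is involved, the safety and mITT sets do not change, and the effect on analysis is at most PP membership. It is worth correcting because the error sits in a safety screen for a drug with hepatic toxicity, and nothing is gained by leaving it.

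The EBV omission is a separate and minor inconsistency, since EBV testing is already required elsewhere in the protocol.

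**What to change.** Delete the antibody-positive branch from the HCV line in 6.3, so that the line asks only for a negative HCV antibody and agrees with exclusion 11. This changes no eligibility criterion and adds no test.

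Only if the sponsor deliberately wants to admit cleared infection should it do the following instead: add an exception for undetectable HCV RNA to exclusion 11 in both 4.2 and the synopsis, modelled on the note to exclusion 10, and replace DNA by RNA in 6.3. This widens eligibility and adds an RNA test for antibody-positive patients, so it is a clinical choice and not a correction.

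As a separate consistency edit, add EBV to footnote 10 of Tables 5 and 6.

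Either route follows the amendment process in Protocol 11.1, with the sponsor classifying the change as substantial or non-substantial under 10.1. The documents do not state accrual status. If recruitment has closed, the edit no longer protects anyone; the remaining step is to check the serology and eligibility listings (SAP 14) for any HCV antibody-positive patient who was dosed, before PP membership is fixed.
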